Rescue medication for hyperglycemia should be prescribed by the investigator at any time it is deemed necessary for the well-being of the subject. During the 12 week treatment period, a review of diet and exercise counseling is suggested prior to prescription of rescue medication in the absence of specific medical indications for rescue medication. Rescue medication is suggested if, after a review of diet and exercise counselling:

1. more than 3 consecutive, daily, fasting SMBG measures are ≥ 270 mg/dL (15 mmol/L) from week 1 to week 6, or ≥ 240 mg/dL (13.3 mmol/L) from week 6 to week 12
2. fasting SMBG values are ≥ 250 mg/dL (13.9 mmol/L) and associated with clinical signs or symptoms of hyperglycemia (e.g. weight loss, blurred vision, increased thirst, or increased urination, or fatigue), and the signs or symptoms are severe

The investigator may provide rescue treatment with any approved medication for diabetes that is not otherwise contraindicated, with the exception of an SGLT2 inhibitor, as study subjects may already be taking a drug in that class as a consequence of being randomized to receive bexagliflozin.

Subjects who receive rescue medication due to poor glycemic control will continue to receive investigational product and standard of care per investigator decision, according to current treatment guidelines. Following the exit visit subjects will be advised to see their primary physician to undergo treatment to control their diabetes.

If hypoglycemia occurs in any subject prescribed rescue medication for hyperglycemia during the study, the total daily dose of the rescue medication should be reduced 50% or more at the discretion of the investigator.

OTHER SAFETY MONITORING ACTIVITIES

The safety monitoring activities will include assessment of vital signs, physical examinations, urinalysis, blood chemistry, hematology, adverse events, and concomitant medication use. The occurrence of blood, liver, or skin disorders will be monitored through laboratory testing and evaluation of adverse event documentation.

Adverse events of special interest as defined in the statistical analysis plan will include any clinical signs and symptoms that indicate adverse experience in the categories listed below. All such events must be appropriately documented within source documentation.

- Genital mycotic infections
- Urinary tract infections including urosepsis and pyelonephritis
- Diuretic effects including hypovolemia
- Hypotension episodes
- Hepatotoxicity

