9.2 Determination of Sample Size

Approximately 320 subjects will be randomized and equally allocated to receive bexagliflozin tablets, 5 mg, 10 mg, 20 mg, or placebo.

The sample size calculation for this study is based on a two group t-test with a two-sided significance at the 5% level and the following assumptions:

- 1) The placebo-corrected population mean change from baseline to Week 12 in HbA1c in the highest dose group of 20 mg will be -0.5%.
- 2) The pooled standard deviation for the change from baseline to Week 12 in HbA1c for the active and placebo groups will be 0.9%.

Under the above assumptions, an estimated sample size of 70 evaluable subjects per treatment arm yields approximately 90% power to detect a treatment difference between bexagliflozin and placebo. A sample size of 80 per arm has been selected to account for a potential drop-out and to allow adequate safety evaluation. The total sample size for this study will be 320 subjects.

This study will be conducted at multiple investigative sites and will likely involve variable numbers of subjects at each site. Enrollment will be on a competitive basis but will be capped at 32 subjects from each site.

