2.2.3 Efficacy Assessments

Efficacy assessments will include blood draws for a glycemic control laboratory panel, including HbA1c and FPG, body weight, and systolic and diastolic blood pressure (BP).

Blood samples for HbA1c and FPG will be obtained at Screening (Visit S1), Run-in (Visit S5), Treatment Period Visits 2, 3, 4 and Follow-up Visit 5. Body weight will be measured at Screening (Visit S1), Washout (Visit S2), Run-in (Visit S5), Treatment Period Visits 2, 3, 4 and Follow-up Visit 5. Supine, sitting and standing

BP measurements will be obtained at Screening (Visit S1), Run-in (Visits S4 and S5), Treatment Period Visits 2, 3, 4 and Follow-up Visit 5.

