Least squares means and the corresponding standard errors for the difference in the changes from baseline over time between each bexagliflozin dose group and placebo will also be presented. Two-sided 95% CIs for the difference in these changes between each active dose and placebo will be generated. P-values from the model effects and key comparisons (i.e., treatment difference at Week 12) will be presented.

- Sensitivity Analyses

The same MMRM model and methods as outlined above for the primary analysis will be repeated using the per protocol analysis set.

Missing Data

The MMRM model is one approach to obtain treatment effect estimates in the presence of missing data. As sensitivity analyses for missing data, the following sensitivity analyses will be performed on the primary efficacy variable for the full analysis set:

- 1) HbA1c values collected after start of rescue medication will be considered missing. Missing HbA1c data (for Weeks 2, 6, or 12) will be imputed through multiple imputation (MI) linear regression methods which assumes a monotone missing data pattern. If the missing data pattern does not follow a monotone missing data then the Markov Chain Monte Carlo (MCMC) method will be used. The covariates to be included in the imputation linear regression model are treatment, center, age, gender, race, BMI, prior anti-diabetic treatment status as well as previous visit HbA1c values. A total of 10 imputed datasets will be generated and then analyzed using the MMRM methods as outlined above for the primary analysis. The point and variance estimates from each of these 10 analyses will be calculated. These analyses results will be combined across the 10 datasets using the standard techniques for multiple imputed data sets through SAS PROC MIANALYZE in order to yield overall treatment comparison results on imputed data.
- 2) Missing HbA1c data will be imputed through last observation carried forward (LOCF), where a subject's prior post-baseline non-missing observation will be imputed for any missing post-baseline visit for which there is a prior non-missing value, and then analyzed using the MMRM methods as outlined above for the primary analysis. HbA1c values collected after the start of rescue medication will be considered missing.
- 3) HbA1c values collected after the start of rescue medication will NOT be considered missing, and the MMRM methods as outlined above for the primary analysis will be re-performed.

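### The imputation model in sensitivity analysis 1 leaves out fasting glucose, on which suggested rescue depends; adding visit FPG is a cheap improvement, with a small expected effect on the result

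*SAP*

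**What the plan says.** **Imputation.** SAP 3.8.1, sensitivity analysis 1, treats HbA1c after the start of rescue as missing and imputes Weeks 2, 6 and 12. Regression imputation is used if the pattern is monotone and MCMC if it is not. The covariates in the "imputation linear regression model are treatment, center, age, gender, race, BMI, prior anti-diabetic treatment status as well as previous visit HbA1c values". Neither FPG nor home glucose is listed. Ten imputed datasets are then analysed with the primary MMRM.

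**Rescue.** Protocol 3.2.3 suggests rescue, after a review of diet and exercise, when "more than 3 consecutive, daily, fasting SMBG measures are" at or above 270 mg/dL (weeks 1 to 6) or 240 mg/dL (weeks 6 to 12). The second criterion is a fasting home value of at least 250 mg/dL with severe signs or symptoms. The investigator may also prescribe rescue at any time on judgement. HbA1c is not a criterion.

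**Data available.** SAP 2.2.3: "Blood samples for HbA1c and FPG will be obtained at Screening (Visit S1), Run-in (Visit S5), Treatment Period Visits 2, 3, 4", and again at the follow-up visit. FPG is therefore measured alongside every scheduled HbA1c.

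**Pre-rescue sample.** Protocol 3.2.3 and 5.6 require a blood sample for HbA1c before rescue is given.

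**The concern.** Imputation under missing at random works when the model contains the variables that drive the missingness. Here part of the missingness is created by rescue, and the suggested criteria for rescue are glucose values. Protocol 3.3 says that HbA1c reflects two to three months of glycemia, so the last HbA1c before rescue only partly shows a recent glucose rise. A model that sees earlier HbA1c but not glucose may therefore predict too low a Week 12 value for a rescued subject. If rescued subjects are more numerous on placebo, the placebo mean is pulled down and every dose-placebo difference shrinks.

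There is also a question of what the analysis is for. The primary MMRM already uses baseline and visit HbA1c, treatment, center and prior treatment. Sensitivity analysis 1 adds only age, gender, race and BMI, so it is likely to agree with the primary result whether or not the shared assumption is right. Auxiliary variables are the main thing that imputation can offer beyond the MMRM, and FPG is the most relevant one collected. The primary objective is to choose dose(s) by comparison with placebo, so the size of the difference matters as well as its significance.

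**Working it through.** **1. The plan's own figure.** Protocol 9.2 is "based on a two group t-test with a two-sided significance at the 5% level". The difference "in the highest dose group of 20 mg will be -0.5"% and the SD "for the active and placebo groups will be 0.9"%.
- n per arm = 2(1.960 + 1.282)² × 0.9² / 0.5² = 68.1, so 69.
- Power at 70 per arm is 0.908 (normal) or 0.904 (noncentral t). This agrees with "an estimated sample size of 70 evaluable subjects per treatment arm yields approximately 90% power".
- Standard error of a difference at 70 per arm: 0.9 × √(2/70) = 0.152.

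The move from 70 to 80 per arm allows for 10/80 = 12.5% loss. The documents give no rescue rate, overall or by arm, and no figure for imputation bias. Everything below rests on assumptions, shown as ranges.

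**2. Hand check of the mechanism.** Assume a correlation of 0.7 between the last HbA1c and Week 12 HbA1c, and 0.6 between FPG and the last HbA1c. Let p be the partial correlation of FPG with Week 12 HbA1c given the last HbA1c. Suppose that the top 5% of placebo subjects on FPG are rescued.
- Mean standardized FPG among those rescued: φ(1.645)/0.05 = 0.1031/0.05 = 2.063.
- The part not explained by HbA1c: √(1 − 0.6²) × 2.063 = 0.8 × 2.063 = 1.650.
- Shortfall in the imputed value: 0.9 × √(1 − 0.7²) × p × 1.650 = 0.643 × p × 1.650. This is 0.21 for p = 0.2 and 0.42 for p = 0.4.

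The simulation below gives 0.236 and 0.469. The excess arises because the regression is fitted only to subjects who were not rescued.

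**3. Simulation with treatment as a covariate** (400,000 per arm, true difference −0.50, FPG omitted). Bias in an arm mean is the rescue proportion times the bias in rescued subjects; the last column is the placebo shift minus the active shift.

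| p | Rescue, placebo/active | Bias, rescued placebo | Placebo mean | Active mean | Difference moves toward 0 by |
|---|---|---|---|---|---|
| 0 | 5%/1% | −0.001 | 0.000 | 0.000 | 0.000 |
| 0.2 | 2%/0.5% | −0.268 | −0.005 | −0.002 | 0.003 |
| 0.2 | 5%/1% | −0.236 | −0.012 | −0.003 | 0.009 |
| 0.2 | 15%/3% | −0.208 | −0.031 | −0.008 | 0.023 |
| 0.4 | 5%/1% | −0.469 | −0.024 | −0.006 | 0.018 |
| 0.4 | 15%/3% | −0.412 | −0.062 | −0.016 | 0.046 |
| 0.4, visit correlation 0.5 | 15%/3% | −0.498 | −0.075 | −0.019 | 0.056 |
| 0.4 | 5%/5% | −0.485 | −0.024 | −0.024 | 0.000 |

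With FPG in the model, the bias in rescued subjects falls to within 0.01. That is the best case by construction, because rescue here depends only on the FPG value supplied to the model.

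**4. Simulation with HbA1c lagging glycemia** (half-time 4.5 to 6 weeks, 30 mg/dL of FPG per 1% HbA1c, placebo rescue 5 to 15%, active 1 to 8%, imputation within arm). Rescued placebo subjects are imputed 0.14 to 0.21 too low when rescue is decided at a visit, and 0.25 to 0.37 too low when it is decided between visits. The difference moves toward zero by 0.006 to 0.035. Adding visit FPG removes the bias in the first case and about 25 to 45% of it in the second.

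**5. Scale.** 0.006/0.152 = 4% and 0.035/0.152 = 23% of one standard error; the extreme case is 0.056/0.152 = 37%. At 70 per arm, t-test power is 0.904 for a difference of 0.50, 0.866 for 0.47 and 0.836 for 0.45.

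**The case against.** **The direction is conditional.** If FPG adds nothing beyond earlier HbA1c (p = 0), there is no bias. If rescue is equally common in both arms, the difference is essentially unbiased. A reader might infer that rescued subjects are certainly imputed too low and sit mainly on placebo. The documents give no rescue by arm and no FPG-HbA1c correlations, so both are plausible inferences only. This stands.

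**Visit FPG is a proxy.** The first suggested criterion is a run of home readings, the second also requires severe signs or symptoms, and rescue is otherwise discretionary. A reader might infer that adding FPG restores missing at random. It does not when rescue starts between visits. This stands, and it limits the benefit of the fix without removing it.

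**The pre-rescue HbA1c helps.** If that sample falls on days 8 to 22 or 36 to 50 it can enter the imputation, and on days 78 to 92 it can serve as the Week 12 value. SAP Table 2 has no window for days 23 to 35 or 51 to 77, however, so under its rules a sample on those days maps to no visit. The between-visit runs placed rescue at Weeks 4 and 9 (about days 29 and 64), inside those gaps, so they show the unfavourable case. The gaps are a visit-window matter that FPG does not cure.

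**Rescue may be rare.** Entry HbA1c is capped at 8.5%, FPG of 250 mg/dL or more at randomization is excluded, and SAP 3.6 counts treatment as rescue only if it is continued for two weeks or longer. The assumed 15% placebo rate may therefore be high.

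**Other analyses exist.** Sensitivity analysis 3 uses observed post-rescue HbA1c, but it answers a different question.

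**Conclusion.** The point holds as a modest weakness of one sensitivity analysis. The imputation model omits the collected variable most closely tied to the suggested rescue criteria, and as written the analysis is a weak check on the primary MMRM. The likely bias in the dose-placebo difference is about 0.006 to 0.035 HbA1c points, up to about 0.05 to 0.06 under heavy assumed rescue on placebo, and about nil with equal rescue. These figures rest on assumed rescue rates, correlations and HbA1c lag.

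A reader might go further and infer that false positive claims are at risk or that the primary analysis is invalid. Neither follows. Where there is bias of this kind, it runs against bexagliflozin. It bears on the estimated size of effect rather than on type I error, and it is a fraction of one standard error. The MMRM shares the assumption, but nothing in the documents shows that it fails by a material amount. This is a cheap improvement.

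**What to change.** In SAP 3.8.1, sensitivity analysis 1, add baseline FPG and FPG at Weeks 2, 6 and 12 to the imputation model as auxiliary variables. Treat FPG collected after the start of rescue as missing, as for HbA1c, and impute it jointly with HbA1c, using MCMC if the pattern is non-monotone. Leave the analysis MMRM unchanged.

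Do not add the last glucose before rescue as a separate covariate. It exists only for rescued subjects, whose later HbA1c is all set to missing, so its coefficient could not be estimated.

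State in the SAP that visit FPG stands in for the home readings and clinical judgement that lead to rescue, so that the result is not read as a full correction.

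**Cost.** A short change to the SAP and a few more variables in the imputation step. No new data are needed. The protocol sets no covariate list for the imputation, so nothing there is contradicted. The downsides are a slightly larger imputation model and more non-monotone missingness, since FPG can itself be missing when a fasting sample is not obtained. The change should be made before unblinding, so that it cannot look data-driven.

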9.5 Analysis of Efficacy

All efficacy analyses will be performed based on the FAS. The primary endpoint analysis will also be conducted using the PP Analysis Set.

For the primary endpoint of HbA1c change from baseline over 12 weeks of treatment, the MMRM analysis of covariance model (ANCOVA) with baseline HbA1c as a covariate will be fitted to the available data, incorporating all visits at which HbA1c was measured for each subject including the scheduled visits at weeks 2, 6, and 12 as well as the unscheduled visits for measurement of HbA1c (National Research Council, 2010). Treatment, study center, and stratification factor for randomization (treatment naïve versus taking one OHA at baseline) will be applied as fixed effects, as will study week and study week-by-treatment interaction. From this model, an estimate of the treatment difference at week 12 will be generated, as will an assessment of whether this estimate is significantly different when comparing placebo with each dose of bexagliflozin at a two-sided 0.05 level of significance. An unstructured within-patient covariance structure will be assumed. HbA1c values obtained after the start of rescue medication will be excluded from this primary analysis.

The MMRM model is one approach to obtain treatment effect estimates in the presence of missing data. As sensitivity analyses for missing data, the following will be performed:

- 3) Missing HbA1c data (for weeks 2, 6, or 12) will be imputed via multiple imputation (MI), following which the MMRM will be repeated on the complete datasets with results combined across complete datasets using standard MI techniques; HbA1c values collected after the start of rescue medication will be considered missing.
- 4) Missing HbA1c data will be imputed via LOCF, following which the MMRM will be repeated; HbA1c values collected after the start of rescue medication will be considered missing.
- 5) HbA1c values collected after the start of rescue medication will NOT be considered missing, and the MMRM analyses will be re-performed.

For the primary efficacy model, a test for a significant baseline-by-treatment interaction will be performed in a separate model, using a 0.100 alpha level. If the baseline-by-treatment interaction is significant, then the ANCOVA assumptions are violated and an analysis of variance (ANOVA) model will be used instead, omitting the baseline covariate.

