3.8.1 Primary Efficacy Endpoint(s)

The primary endpoint is HbA1c change from baseline through 12 weeks, and the primary analysis is based on the available data and data obtained after rescue will be excluded and considered missing. Mixed model repeated measures (MMRM) analysis of covariance model (ANCOVA) with baseline HbA1c as a covariate will be fit to the available data, incorporating all visits at which HbA1c was measured for each subject including scheduled visits at Weeks 2, 6, and 12 as well as unscheduled visits for measurements of HbA1c. Treatment (placebo, 5 mg, 10 mg, 20 mg), study center, prior anti-diabetic treatment status, study visit and treatment-by-visit interaction will be applied as fixed effects and subject as a random effect.

A normal distribution will be assumed for the built-in probability distribution. Model assumption will be checked. An unstructured (UN) within-subject covariance structure will also be assumed. The Kenward-Roger approximation will be used to estimate the denominator degrees of freedom.

Sample SAS code for this analysis is as follows:

```
proc mixed data=temp method=reml covtest;  
  class subject visit treat prior center;  
  model change = visit treat prior center baseline visit*treat /  
  solution ddfm=KENWARDROGER;  
  repeated visit / subject=subject type=un;  
  lsmeans visit*treat / diff=all cl alpha=0.05;  
run;
```

In the case that this covariance matrix is not an appropriate estimate, other covariance structures (e.g., compound symmetry) will be considered and ultimately determined through graphical tools (i.e., plot of changes in covariance and correlation among residuals on the same subject over lag between times of observation) and information criteria [e.g., Akaike's Information Criteria (AIC)].

Descriptive statistics will be presented for the observed measurements as well as for change from baseline by treatment group and visit overall (all subjects) and by country.

Least squares (LS) means and the corresponding standard errors (SE) of the change from baseline over time will be presented by treatment. In addition, the time profile of these LS mean and SE values will be presented graphically.

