Dropout patterns may be assessed by graphical methods (e.g., Kaplan-Meier plot for time to drop-out).

- Tests for Interaction

For the primary efficacy model, specifically the MMRM ANCOVA model, a test for a significant treatment-by-baseline interaction will be performed in a separate model. If the treatment-by-baseline interaction is significant at an $\alpha=0.100$, then an analysis of variance (ANOVA) model will be used instead, removing the baseline covariate.

A treatment-by-study center interaction term will be added to the MMRM ANCOVA (or ANOVA) model used for the analyses of the primary efficacy variable. If a statistically significant treatment-by-study center interaction effect is observed at a 0.100 level, then separate analyses may be performed for each study center.

A treatment-by-country interaction term will be added to the MMRM ANCOVA (or ANOVA) model used for the analyses of the primary efficacy variable. A statistically significant treatment-by-country interaction effect will be declared at the 0.100 level. Separate analyses will be performed for each country.

Note that significant interactions, if only quantitative (and not qualitative) in nature, will not necessarily preclude data being pooled across the baseline covariate or across study centers for the primary analysis.

- Dose Response

A dose response analysis on the change from baseline in HbA1c to Week 12 for the full analysis set will be conducted. Mean change from baseline in HbA1c to Week 12 (on vertical axis) will be presented graphically by dose group (on horizontal axis). Assessments of linear and quadratic dose-response trends across dose groups will be constructed using the MMRM ANCOVA model used for the primary efficacy analysis with appropriate orthogonal polynomial contrasts. P-values for each orthogonal polynomial contrast will be presented. To account for the unequal spacing of the dose levels (0, 5, 10 and 20), the coefficients to be used for the contrasts are as follows:

Linear:	-0.591608	-0.253546	0.0845154	0.7606388
Quadratic:	0.5640761	-0.322329	-0.644658	0.4029115

The coefficients are derived based on the statistical method from Robson, D.S. 1959: A simple method for constructing orthogonal polynomials when the independent variable is unequally spaced. *Biometrics* 15(2): 187-191.

Additional models may be considered if the dose response curve appears to be highly influenced by any single dose group.

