3.8.2 Secondary Efficacy Endpoints

The secondary efficacy endpoints, fasting plasma glucose, sitting systolic and diastolic blood pressure and weight, will be analyzed using the same MMRM ANCOVA model used for the primary efficacy analysis on the full analysis set. In addition, for each secondary efficacy endpoint, the least squares means and standard errors of the change from baseline over time by treatment group will be presented graphically. Sensitivity analyses will not be performed on the secondary efficacy endpoints.

For each subject, post-baseline HbA1c values will be reviewed and subjects with at least one post-baseline HbA1c value $<7\%$ will be flagged. HbA1c values obtained after start of rescue medication will be excluded from this analysis. The number and percentage of subjects with at least one HbA1c value $<7\%$ will be summarized by treatment group for the full analysis set. A logistic model will be used to characterize treatment differences in the proportions of subjects with at least one post-baseline HbA1c value $<7\%$. For this model, the dependent variable will take values of $1 = '<7\%'$ or $0 = '≥7\%'$ and the predictor variables will include treatment, study center, baseline HbA1c and prior anti-diabetic treatment status. Odds ratio for the treatment difference versus placebo, its 95% confidence interval and the associated p-value will be presented.

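### A treatment-by-baseline p-value below 0.10 removes baseline HbA1c from the primary model, which does not address unequal slopes and modestly reduces precision

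*SAP*

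**What the plan says.** The primary analysis is an MMRM on change in HbA1c with baseline HbA1c as covariate. The sample code in SAP 3.8.1 has "model change = visit treat prior center baseline visit*treat", that is, one baseline slope shared by all arms and visits.

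Under Tests for Interaction, the treatment-by-baseline term is examined in a separate model. If it is significant at 0.100, "then an analysis of variance (ANOVA) model will be used instead, removing the baseline covariate". Protocol 9.5 gives the reasoning: "then the ANCOVA assumptions are violated and an analysis of variance (ANOVA) model will be used instead, omitting the baseline covariate".

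Three further statements bear on the rule:

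- A closing note in the same SAP subsection says that interactions that are only quantitative "will not necessarily preclude data being pooled across the baseline covariate or across study centers for the primary analysis".
- The center and country interaction tests are to be run in whichever of the ANCOVA or ANOVA is in force. The dose-response trends are "constructed using the MMRM ANCOVA model used for the primary efficacy analysis with appropriate orthogonal polynomial contrasts", with no ANOVA alternative.
- In SAP 3.8.2, FPG, blood pressure and weight "will be analyzed using the same MMRM ANCOVA model used for the primary efficacy analysis on the full analysis set".

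The sample size in Protocol 9.2 rests on a "two group t-test with a two-sided significance at the 5% level" and assumes: "The pooled standard deviation for the change from baseline to Week 12 in HbA1c for the active and placebo groups will be 0.9" (percentage points).

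**The concern.** A treatment-by-baseline interaction means that the treatment effect varies with starting HbA1c. Omitting baseline does not represent that; it moves the unequal slopes into the residual. If heterogeneity matters, the useful response is to describe it. If it does not, the common-slope ANCOVA already estimates the average effect without bias under randomisation.

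The rule is prespecified, but its trigger is a test on unblinded outcome data, and at the 0.100 level it is met by chance in about one trial in ten. The plan also gives reason to expect some dependence on baseline: Protocol 3.3 argues that the link between glucosuria and HbA1c change weakens at high baseline values. The SAP gives no code for the interaction test. If a two-way term is added to the sample code, it is averaged over Weeks 2, 6 and 12 and need not reflect Week 12.

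The wording adds two uncertainties. The switch is stated as mandatory, yet the note on quantitative interactions softens it without a criterion, so two statisticians could reach different primary models from the same data. And after a switch, the ANCOVA named for the dose-response contrasts is no longer the primary model. In a dose-finding trial, the pairwise tests and the dose-response contrasts should rest on one model.

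**Working it through.** **Inputs.** From the documents: SD 0.9, difference 0.5, 70 evaluable and 80 randomised per arm, two-sided 5% (Protocol 9.2); baseline HbA1c 7.0 to 8.5% (Protocol 4.2); trigger 0.100 (SAP 3.1.3 and 3.8.1). The baseline distribution, slopes, visit profiles and correlations are not given and are assumptions. Baseline is taken as uniform, so its variance is 1.5²/12 = 0.1875 and its SD 0.433.

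**1. The plan's own figure.** SE = 0.9 × √(2/70) = 0.152; noncentrality = 0.5/0.152 = 3.29; the t-test on 138 df has power 0.904. The stated figure of about 90% is reproduced, and it uses no baseline adjustment.

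**2. Week 12 only, common slope.** R² = (slope × 0.433/0.9)². Omitting baseline multiplies the variance by 1/(1 − R²).

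| Slope | R² | Variance ratio | SE ratio | Power at 70 per arm, baseline kept |
|---|---|---|---|---|
| −0.3 | 0.021 | 1.021 | 1.011 | 0.910 |
| −0.5 | 0.058 | 1.061 | 1.030 | 0.920 |
| −0.7 | 0.113 | 1.128 | 1.062 | 0.934 |

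Power without baseline is 0.904 in each row.

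**3. Unequal slopes, constant over visits.** Take placebo −0.5 and all active arms −1.0. The residual variance is 0.81 − 0.25 × 0.1875 = 0.763, and the common slope is (−0.5 − 3 × 1.0)/4 = −0.875.

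- Without baseline: 0.810 + (0.763 + 1.0² × 0.1875) = 1.761.
- With the common slope: (0.763 + 0.375² × 0.1875) + (0.763 + 0.125² × 0.1875) = 1.556.
- Ratio 1.132. The ANOVA is less precise even though the slopes truly differ.

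**4. Slopes that grow over visits.** The SAP model has a single slope, so early visits dominate its estimate. Take the same Week 12 slopes, reached as 25/65/100% at Weeks 2, 6 and 12, with visit SDs 0.3/0.6/0.9 and residual correlations 0.8 (adjacent visits) and 0.6 (Weeks 2 and 12). The generalised least squares weights on the three visits are about 1.34, −0.33 and 0.00, so the fitted slope is only about −0.10.

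- With baseline: (0.763 + 0.40² × 0.1875) + (0.763 + 0.90² × 0.1875) = 1.708.
- Ratio 1.761/1.708 = 1.031.

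Variance of 20 mg versus placebo without baseline, relative to the SAP model, over placebo slopes −0.3 or −0.5 and extra active slopes 0, −0.3 or −0.5:

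| Slope profile (visit SDs) | Variance increase |
|---|---|
| 25/65/100% (0.3/0.6/0.9) | 0.5% to 3.1% (SE 0.2% to 1.5%) |
| 50/80/100% (0.54/0.72/0.9) | 1.6% to 10.7% |
| Constant | 2.1% to 13.2% (SE 1.1% to 6.4%) |

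At an assumed SD of 0.7, the first profile gives 0.8% to 4.9% and the last 3.6% to 22%.

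**5. Behaviour of the two-step rule.** Simulation used complete data, with center and prior treatment omitted: 3,000 trials per scenario at 80 per arm, and 2,500 per scenario at 70 per arm for power.

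- Trigger rate: 10–12% with no interaction, 12–26% if the Week 12 slope differs by 0.3 between active and placebo, 16–55% if it differs by 0.5.
- Bias: at most 0.004 for either model.
- Type I error of the two-step rule: 0.042–0.057 (Monte Carlo SE 0.004).
- Power for a difference of 0.5: 0.90–0.91 for the ANOVA with no interaction. With the slopes of step 3, 0.89 under the rule and 0.92 if baseline is kept. With the 25/65/100% profile, 0.88 and 0.89.

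**The case against.** The strongest reply is that little follows from the rule. It is prespecified, type I error is intact, and the trial was sized on an unadjusted t-test, so the fallback is no weaker than the planned analysis when there is no interaction. All of that stands.

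The larger penalties need baseline slopes at full size by Week 2. Since HbA1c reflects two to three months of glycaemia (Protocol 3.3), growing slopes are more plausible, and there the SE cost is at most 1.5%. That limits the size but does not change the direction.

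The ANOVA is not always worse. With a placebo slope of opposite sign to the active slopes, a Week 12 simulation gave it the smaller SE (0.154 against 0.155), but its power was no higher (89.5% against 89.7%). This is an extreme case and a negligible gain.

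The unbiasedness result assumes complete data. Checks with assumed missingness disagreed on whether keeping baseline reduces bias, so the conclusion does not rest on that argument.

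The note on quantitative interactions can be read as qualifying the switch. Without a criterion, it makes the primary model uncertain instead.

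For the secondary endpoints, the natural reading is that they keep the ANCOVA, because the switch is written for the primary model only. That ambiguity is minor; the one for the dose-response contrasts is real.

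**Conclusion.** The concern holds. Removing baseline HbA1c is the wrong response to unequal slopes: it models nothing, removes no bias under randomisation, and in every plausible scenario examined costs some precision. The loss is modest: 0.5% to 13.2% in variance at SD 0.9, most likely towards the lower end if slopes build up over the visits. Power falls by at most about 3 points in the least favourable case tested. Type I error is unaffected, and planned power is kept if there is no interaction and 0.9 is the unadjusted SD. The direction is well supported; the size depends on slopes, visit profiles and a baseline distribution that the documents do not give. The unclear status of the switch, and of the model behind the dose-response contrasts, is a separate reason to change the text and does not depend on those assumptions. The change should be made, as a free improvement.

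**What to change.** - Delete the switch to ANOVA in SAP 3.8.1 and the matching sentence in Protocol 9.5. Keep baseline HbA1c in the primary model whatever the interaction test shows.
- Use that same model for the sensitivity analyses and the dose-response contrasts. Use the same model form for the secondary endpoints, with each endpoint's own baseline as covariate. Drop the ANOVA alternative from the center and country tests.
- Remove the reference to the baseline covariate from the note on quantitative interactions.
- Report the treatment-by-baseline interaction at Week 12 as supportive, for example from a model with treatment-by-baseline-by-visit terms. Give treatment differences at the overall mean baseline and at stated values such as 7.25% and 8.25%.

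The cost is SAP wording and one protocol passage. No new data and no change in sample size are needed.
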